
For AML Part 3b and Part 4, each dose cohort will initially enroll 3-4 subjects and up to 10 subjects per cohort may be enrolled. After reviewing all available safety and tolerability data, dose level decisions (eg, escalation/de-escalation/expansion) will be made by the DLRT using a modified Toxicity Probability Interval (mTPI) model (Ji et al, 2010) based on all subjects that have been enrolled at current dose. Dose escalation is considered to be complete if one of the following rules is met:

- The highest planned dose level is evaluated, MTD/MTCD has not been defined and no DLTs occur at any dose level. In this case the maximum administrated dose (MAD) may be used for phase 2.
- An MTD/MTCD is identified.

Guidelines for dose level decisions can be found in [Table 4-2](#). Details regarding the mTPI model and dose finding are described in Section [11.16](#). Please note one exception to the guidelines provided in [Table 4-2](#), a single grade 3 treatment-related troponin elevation will result in dose de-escalation regardless of number of subjects treated at current dose.

Table 4-2. Guidelines for Dose-level Decisions for Part 3b and Part 4

No. of DLT-evaluable ^a subjects treated at current dose	Number of DLTs		
	Escalate	Stay at current dose	De-escalate ^b
3	0	1	≥ 2
6	0-1	-	≥ 2
9	0-1	2	≥ 3
10 ^c	0-1	2-3	≥ 4

DLT = dose-limiting toxicity

^a A subject is considered DLT-evaluable if he/she experienced a DLT during the DLT evaluation period or if he/she received 75% of the planned doses of AMG 176 and completed the DLT evaluation period.

^b De-escalate guideline applies only when current dose level and enrollment is allowed to a lower dose level.

^c The maximum number of evaluable subjects at one dose level is 10.

The MTD/MTCD is defined as the highest dose with a probability of DLT lower than or close to a targeted toxicity probability of 0.2.

For the first dose level and at each new higher dose level, the first enrolled subject will be treated, and then after a period of 72 hours, subsequent subjects will be treated, provided that there are no significant toxicities relating to the treatment of the first subject.

In addition to safety, efficacy of complete remission per ELN in Part 4 will be evaluated. At MTCD or optimal biological dose (OBD), 1 complete remission out of 6 subjects, or 2 complete remissions out of 10 subjects are expected.

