11.16 Appendix 16. Modified Toxicity Probability Interval Design

A modified Toxicity Probability Interval (mTPI) design will be used to guide dose exploration. The MTD is defined as the highest dose with a probability of DLT lower than or close to a targeted toxicity probability of 0.2. The doses are considered close to the MTD if the toxicity probabilities belong to the proper dosing interval [0.15, 0.25] which corresponds to staying at the current dose (S). The underdosing interval is defined as (0, 0.15) in which the doses are deemed lower than the MTD and corresponds to a dose escalation (E). The overdosing interval is (0.25, 1) in which the doses are deemed higher than the MTD and corresponds to a dose de-escalation (D).

The dose-finding decisions are guided based on Bayesian decision rule by minimizing the posterior expected loss through calculating the unit probability mass (UPM). At each dose level, the UPM is computed for the dosing intervals using the observed data enrolled at current dose. The dose-finding decision is determined as the interval with maximum UPM. A set of independent and non-informative prior Beta (0.5, 0.5) is used for each dose level, which provides equal prior expected loss for the decisions (Ji et al, 2010). Dose escalation will not occur unless at least 6 subjects are treated at the current dose level. In addition, any dose whose posterior probability of toxicity is greater than the target toxicity exceeds 80% will be considered as unacceptable toxicity. This dose and higher doses will not be used again in the trial. Dose exploration will continue until either the maximum number of subjects for Part 3b (n = 11 subjects) and Part 4 (n = approximately 60 subjects) are treated or all doses are determined to be intolerable.

Operating Characteristics

The operating characteristics of the mTPI were evaluated via simulations. The cohort size was fixed to 6 subjects. A total of 3 dose levels were considered for AML Part 3b and 4 dose levels were considered for AML Part 4.

For Part 3b, the design was evaluated for 3 possible dose-response scenarios: Low, Middle, and High MTD. For Part 4, the design was evaluated for 4 possible dose-response scenarios: Low, Middle, and High MTD. [Table 11-5](#) and [Table 11-7](#) show the dose level and true probability of DLT for each scenario used in the simulated studies estimating the MTD. [Table 11-6](#) and [Table 11-8](#) report the operating characteristics from 1 000 simulated studies.

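### Table 11-8 (Part 4 operating characteristics) was not simulated under the plan's cap of 10 evaluable subjects per dose level: four levels allow at most 40 subjects, but the table reports medians of 50

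*Protocol*

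**What the plan says.** **The dose-finding rule for conduct.** For Part 3b and Part 4, Protocol Section 4.1.1 starts each dose cohort with 3-4 subjects and says that "up to 10 subjects per cohort may be enrolled". Table 4-2 permits escalation with 0 DLTs in 3 evaluable subjects. Its footnote c reads "The maximum number of evaluable subjects at one dose level is 10". SAP Section 3.3 and SAP Table 2 repeat the starting number, the boundaries and the cap.

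**The rule in Appendix 16.** The text adds a condition that Table 4-2 lacks: "Dose escalation will not occur unless at least 6 subjects are treated at the current dose level". The only sample-size stop it gives is an overall one, namely when the "maximum number of subjects for Part 3b (n = 11 subjects) and Part 4 (n = approximately 60 subjects) are treated". It does not mention a limit per dose level.

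**The simulation.** Appendix 16 states "The cohort size was fixed to 6 subjects" and, for the number of doses, "A total of 3 dose levels were considered for AML Part 3b and 4 dose levels were considered for AML Part 4". The tables are said to "report the operating characteristics from 1 000 simulated studies".

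**The reported result.** Table 11-8 gives the number of subjects per simulated Part 4 study as median (IQR): Low 36 (6, 50), Middle 50 (48, 50), High 50 (50, 50).

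**The concern.** Table 11-8 is the only place in either document that says how often the Part 4 rule selects each dose, how many subjects it uses and how many DLTs it produces. A reader will take it as the performance of the rule in Section 4.1.1. If the simulated rule let more subjects accumulate on a dose than the plan allows, the table describes a procedure with more information per dose than the trial could have had. Its selection percentages and DLT counts would then not carry over. What is at stake is whether the table can be cited, in the study report or in support of the combination dose, as a property of the planned design.

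**Working it through.** **1. The bound (exact)**
- Inputs: cap of 10 per dose level (Protocol Table 4-2 and SAP Table 2, footnote c); 4 dose levels (Appendix 16).
- Largest possible study: 4 x 10 = 40.
- Table 11-8: median 50 in Middle and High, upper quartile 50 in Low, Middle and High.
- 50 / 4 = 12.5, so a 50-subject study has at least 13 subjects on one dose. Reaching 50 under the cap would take 5 dose levels.

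This step needs no simulation and no assumption about how the MTD is chosen.

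**2. Could the excess be non-evaluable subjects?**
Appendix 16 describes none. In High, the median DLT count is 6 and the median proportion is 12.0%: 6 / 50 = 12.0%. The upper quartile agrees too: 8 / 50 = 16.0%. All 50 subjects are in the DLT denominator.

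**3. The other mismatches, side by side**

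| Item | Section 4.1.1, Table 4-2, SAP 3.3 | Appendix 16 and Table 11-8 |
|---|---|---|
| Limit per dose | 10 evaluable | not mentioned; at least 13 in a 50-subject study |
| Cohort size | 3-4 initially | 6 |
| Earliest escalation | 0 DLTs in 3 | at least 6 treated |
| Total for Part 4 | approximately 60 (Section 4.2; SAP 3.2) | Appendix 16 text approximately 60; table reaches 50 |

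The amendment history records an earlier Part 4 maximum of 50. That may be where the 50 comes from, but this is only a possible explanation.

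**4. Simulation check**
Settings: mTPI with Beta(0.5, 0.5) prior, interval limits 0.15 and 0.25, exclusion of a dose when P(DLT rate > 0.20) exceeds 80%, minimum 6 before escalation, cohorts of 6, total 50. Assumption: a study stops when the next dose is full. With the exclusion rule included, this decision rule reproduces every boundary in Table 4-2.

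Median (IQR) subjects:

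| Per-dose limit | Low | Middle | High |
|---|---|---|---|
| Table 11-8 | 36 (6, 50) | 50 (48, 50) | 50 (50, 50) |
| none | 50 (6, 50) | 50 (50, 50) | 50 (50, 50) |
| 42 | 48 (6, 50) | 50 (48, 50) | 50 (50, 50) |
| 30 | 36 (6, 42) | 42 (36, 48) | 48 (42, 48) |
| 10 (the plan) | 16 (6, 22) | 22 (16, 28) | 28 (22, 28) |

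No limit tried reproduces all three columns. The cap of 10 is far from all of them. Raising the total to 60 does not change the capped medians.

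**5. Selection percentages (illustrative only)**
In Low, Dose Levels 2-4 have a true DLT rate of 0.30 or more. The table's rows for them add to 9.29 + 0.47 + 0.03 = 9.79%. Without a per-dose limit, simulation gives about 7-10%. With the cap of 10 it gives roughly 16-27%, depending on the MTD-selection rule and the cohort size, neither of which is settled by the text. Most of the rise is at Dose Level 2. The cap also has favourable effects: in Low, mean DLTs per study fall from 8.0 to 3.9, and in High, selection of Dose Level 4 (true rate 0.20) rises, for example from 33% to 43%.

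**6. Entries that cannot be right as printed**
- With 1,000 studies, one study is 0.1%, so 9.29%, 0.47% and 0.03% cannot occur; 0.03% would be 0.3 of a study.
- High, lower quartile of the DLT proportion: printed 1.0%, but the lower quartile of the DLT count is 4, and 4 / 50 = 8%.
- "For Part 4, the design was evaluated for 4 possible dose-response scenarios: Low, Middle, and High MTD": four scenarios announced, three named and tabulated.

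**The case against.** The strongest reply is that little depends on the table. Protocol Section 9.2 and SAP Section 3.2 base the sample size on practical considerations. Dose decisions go through the dose-level review team. No DLT had been seen in the 22 Part 4 subjects enrolled by November 2022 (Protocol Section 2.1). The SAP does not reproduce Table 11-8, and its Section 10 says that the study was terminated early and that only a synopsis report with selected analyses will follow. The planned total also fits the cap: four weekly cohorts plus 5a and 5b make six, and 6 x 10 = 60. All of this stands and lowers the weight of the point. It does not rescue the table, which is stated to simulate four levels.

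Three stronger readings are tempting and are not supported.

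- **That the simulated design was uncapped.** At least 13 on one dose rules out a cap of 10, but not every limit. The unlimited runs miss the table in places: Low median 50 against 36, Middle lower quartile 50 against 48, and no dose selected in about 3% of High studies against the 11.9% implied by the table (100 minus its four rows). A limit of 42 matches the Middle and High subject counts.
- **That enrolment counts prove the minimum of 6 was not followed.** One can argue that Part 3b needed 6 + 6 = 12 subjects before its third dose against 11 enrolled, and that Part 4 needed 3 x 6 + 6 = 24 against the 21-22 reported with 6 at the fourth weekly dose. Both sums assume that each subject counts once, at one dose. Table 2-1 lists 5 + 5 + 4 = 14 Part 3b weekly monotherapy subjects against 11 enrolled, and Sections 4.1.1 and 6.1.1 let subjects move between doses.
- **That the plan understates selection of over-toxic doses by a known amount.** The 16-27% range rests on unstated rules, applies only to Low (Middle and High contain no dose above 0.25), and comes from a simulator that does not reproduce the table's High column.

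**Conclusion.** The point holds in this form: Table 11-8 was not generated under the plan's cap of 10 evaluable subjects per dose level. The margin is exact, 40 possible against 50 reported, and rests only on the stated cap and the stated four levels. The cohort size and the minimum before escalation in Appendix 16 also differ from Section 4.1.1, Table 4-2 and SAP 3.3; that conflict stands on the text alone. The table's sample sizes, DLT counts and selection percentages are therefore not the operating characteristics of the planned Part 4 rule. Which limit was simulated cannot be told from the documents.

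The proof by arithmetic is specific to Part 4. Table 11-6 (Part 3b) reports 20 subjects over three levels, within 3 x 10 = 30.

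Severity is minor. No remaining dose decision shown in the documents depends on the table, and nothing here suggests that a dose decision already taken was wrong.

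**What to change.** 1. Confirm from the simulation code which per-dose limit, cohort size, escalation minimum and total were used for Table 11-8.
2. Reconcile Appendix 16 with Section 4.1.1, Table 4-2 and SAP 3.3 on the cap, the cohort size, the minimum before escalation and the Part 4 total. This review does not say which rule is right.
3. Re-run and replace Table 11-8 under the reconciled rules. State how the MTD is selected, what happens when a dose is full, and how a study is counted if it ends at the top dose with the decision still to escalate. Correct the two-decimal percentages or the replicate count, the 1.0 quartile and the number of scenarios at the same time.
4. Alternatively, since the study was terminated early, state in the study report that Table 11-8 was not simulated under the cap of 10 and should not be cited as the properties of the planned rule. The report should not call the simulated design uncapped unless the code confirms it.

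Cost: a few hours of simulation and one replacement table, or a short statement in the report.

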[figure not shown]

Amendment 3 (v4.0)	12NOV2024	

Updates made based on protocol amendment 16

QD2 updated to BIW.

Added part 5 (BIW) objective and endpoint; also added exploratory objective and endpoints.

Updated text in the study design.

Updated sample size

Updated definition of overall response rate for MM and AML.

Added dose intensity and relative dose intensity in definition and exposure to investigational product and non-investigational product.

Censoring rule for PFS has been updated in definition.

Interim efficacy analysis set added in section 6.7.1.

Included the text "Interim safety analyses will be performed to support the evaluation of safety by the DLRT" in section 7.1.

Added additional interim analyses information in section 7.1.

	

• Added Exploratory endpoint in the section 9.5.3

• Updated the layout in section 9.6.1

• Updated MedDRA version from 24.0 to 26.1

• Added details in section 9.6.9

• Added details in section 9.6.10

• Added Appendix B

• Updated section 10 Changes From Protocol-specified Analyses

--	--

## List of Abbreviations

Abbreviation or Term	Definition/Explanation
ALP	alkaline phosphatase
ALT	alanine aminotransferase
AML	acute myeloid leukemia
AST	aspartate aminotransferase (SGOT)
AUC	area under the concentration-time curve
AUC 0-168 hr	area under the concentration-time curve from 0 to 168 hours
BAK	B-cell receptor associated kinases
BAX	B-cell lymphoma/leukemia 2 associated X protein
BCL2	B-cell lymphoma/leukemia 2
BCL2-L1	BCL2 like 1
BCL-XL	B-cell lymphoma extra large
BIW	twice weekly
CL	Clearance
C max	maximum observed concentration
C min	minimum observed concentration
COVID-19	coronavirus disease 2019
CPMS	clinical pharmacology modeling and simulation
CR	complete response
CrCl	creatinine clearance
CRI	incomplete hematologic recovery; complete response/remission with incomplete recovery of peripheral blood counts
CRF	case report form
CRO	contract research organization
CT	computed tomography
CTCAE	Common Terminology Criteria for Adverse Events
CYP3A4	Cytochrome P450 3A4
DDI	drug-drug interaction
DLRM	dose-level review meeting
DLRT	dose-level review team
DLT	dose-limiting toxicity
DOR	duration of response
DBP	diastolic blood pressure
ECG	electrocardiogram
ECHO	echocardiogram

Abbreviation or Term	Definition/Explanation
ECOG	Eastern Cooperative Oncology Group
eCRF	electronic case report form
EFS	event free survival
ELN	European LeukemiaNet
FAS	Full Analysis Set
FIH	first in human
FISH	fluorescent in situ hybridization
FSH	follicle stimulation hormone
heart rate/HR	number of cardiac cycles per unit of time
IMWG	International Myeloma Working Group
IMWG-URC	International Myeloma Working Group - Uniform Response Criteria
IQR	interquartile range
IV	intravenous or roman numeral 4
MCL1	myeloid cell leukemia sequence 1
MedDRA	Medical Dictionary for Regulatory Activities
MFI	medium fluorescent intensity
MLFS	morphologic leukemia free state
MM	multiple myeloma
MRD	minimal residual disease
MRD[-]	minimal residual disease negativity
MTCD	maximum tolerated combination dose
MTD	maximum tolerated dose
mTPI	modified Toxicity Probability Interval
MUGA	multigated acquisition scan
OBD	optimal biological dose
OR	overall response
OS	overall survival
PD	pharmacodynamics
PFS	progression free survival
PK	Pharmacokinetics
PR	partial response
PR interval	PR interval is measured from the beginning of the P wave to the beginning of the QRS complex in the heart's electrical cycle as measured by ECG or partial response
QRS	QRS interval is the interval between the Q wave and the S wave in the heart's electrical cycle as measured by ECG; represents the time it takes for the depolarization of the ventricles

Abbreviation or Term	Definition/Explanation
QT	QT interval is a measure of the time between the start of the Q wave and the end of the T wave in the heart's electrical cycle as measured by ECG
QTc	QT interval corrected for heart rate using accepted methodology
QTcF	QT interval corrected for heart rate using Fridericia's formula
QW	once weekly
R/R	relapsed or refractory
RP2D	recommended phase 2 dose
RUNX1	runt-related transcription factor 1
SBP	systolic blood pressure
SC	subcutaneous(ly)
sCR	stringent complete response
Screen	Screening
SD	standard deviation
SFU	safety follow-up
SOC	standard of care
$t_{1/2}$	half-life
$t_{max}$	time of maximum observed serum concentration
TLS	tumor lysis syndrome
ULN	upper limit of normal
UPM	unit probability mass
US	United States
VGPR	very good partial response
WHODRUG	World Health Organization Drug

## 1. Introduction

The purpose of this Statistical Analysis Plan (SAP) is to provide details of the statistical analyses that have been outlined within the protocol for study 20150161, AMG 176 dated **13 July 2023**. The scope of this plan includes the primary analysis and the final analysis that are planned and will be executed by the Amgen Global Biostatistical Science department unless otherwise specified.

## 2. Objectives, Endpoints and Hypotheses

### 2.1 Objectives and Endpoints

Objectives	Endpoints
Primary	
Multiple Myeloma Part 1a (BIW)	

Evaluate the safety and tolerability of AMG 176 monotherapy in subjects with relapsed or refractory multiple myeloma (MM) and determine the maximum tolerated dose (MTD) for twice weekly (BIW) dosing schedule

Evaluate the pharmacokinetics (PK) of AMG 176 when administered as monotherapy (BIW)

	

Incidence of Dose-Limiting Toxicities (DLTs), treatment-related and treatment-emergent adverse events, and clinically significant changes in vital signs, electrocardiograms (ECGs), and clinical laboratory tests

PK parameters for AMG 176, including, but not limited to, maximum observed concentration (<math>C_{max}</math>), area under the concentration-time curve (AUC), clearance (CL), and half-life (<math>t_{1/2}</math>)

Multiple Myeloma Part 1b (QW)	

Evaluate the safety and tolerability of AMG 176 monotherapy in subjects with relapsed or refractory MM and determine the MTD for a once weekly (QW) dosing schedule

Evaluate the PK of AMG 176 when administered as monotherapy (QW)

	

Incidence of DLTs, treatment-related, treatment-emergent adverse events and clinically significant changes in vital signs, ECGs, and clinical laboratory tests

PK parameters for AMG 176 including, but not limited to <math>C_{max}</math>, AUC, CL, and <math>t_{1/2}</math>

Acute Myeloid Leukemia Part 3a (BIW)	

Evaluate the safety and tolerability of AMG 176 monotherapy in subjects with relapsed or refractory acute myeloid leukemia (AML) and determine the MTD for BIW dosing as a monotherapy in subjects with relapsed or refractory AML

Evaluate the PK of AMG 176 when administered as monotherapy (BIW)

	

Incidence of DLTs, treatment-related, treatment-emergent adverse events and clinically significant changes in vital signs, ECGs, and clinical laboratory tests

PK parameters for AMG 176 including, but not limited to <math>C_{max}</math>, AUC, CL, and <math>t_{1/2}</math>

Acute Myeloid Leukemia Part 3b (QW)	
• Evaluate the safety and tolerability of AMG 176 QW monotherapy in subjects with relapsed or refractory AML	• Incidence of DLTs, treatment-related, treatment-emergent adverse events and clinically significant changes in vital signs, ECGs, and clinical laboratory tests
• Evaluate the PK of AMG 176 when administered as monotherapy (QW)	• PK parameters for AMG 176 including, but not limited to $C_{max}$ , AUC, CL, and $t_{1/2}$
Acute Myeloid Leukemia Part 3c (QW) in Japan	
• Evaluate the safety and tolerability of AMG 176 QW monotherapy in subjects in Japan with relapsed or refractory AML	• Incidence of DLTs, treatment-related, treatment-emergent adverse events and clinically significant changes in vital signs, ECGs, and clinical laboratory tests
• Evaluate the PK of AMG 176 when administered as monotherapy (QW) in Japan	• PK parameters for AMG 176 including, but not limited to $C_{max}$ , AUC, CL, and $t_{1/2}$
Acute Myeloid Leukemia Part 3d - Drug-drug Interaction (DDI) Assessment with Itraconazole in United States (US)	
• Evaluate the PK of AMG 176 when given alone and in combination with itraconazole in subjects with AML	• PK parameters for AMG 176 including, but not limited to $C_{max}$ , AUC, CL, and $t_{1/2}$
Acute Myeloid Leukemia Parts 4 and 5 (QW, BIW, and conventional AML dosing) in combination with azacitidine	
• Evaluate the safety and tolerability of AMG 176 in combination with azacitidine in subjects with relapsed or refractory AML and in Part 4 only , determine the maximum tolerated combination dose (MTCD) of AMG 176 in combination with azacitidine	• Incidence of DLTs ( Part 4 only ), treatment-related, treatment-emergent adverse events and clinically significant changes in vital signs, ECGs, and clinical laboratory tests
• Evaluate the PK of AMG 176 and azacitidine when administered in combination	• PK parameters for AMG 176 and azacitidine including, but not limited to, $C_{max}$ , AUC, CL, and $t_{1/2}$
Secondary	
Multiple Myeloma Part 1a (BIW)	
• Demonstrate inactivation of myeloid cell leukemia sequence 1 (MCL1) by the increase of active B-cell lymphoma/leukemia 2 associated X protein (BAX) and caspase 3 in circulating monocytes and/or the decrease of circulating monocytes in AMG 176 BIW treated subjects	• BAX and caspase 3 expression in circulating monocytes and/or circulating monocyte counts
• Evaluate preliminary efficacy of AMG 176 BIW when given as monotherapy in relapsed or refractory MM	• Overall response (OR) according to International Myeloma Working Group uniform response criteria (IMWG-URC) for MM subjects, progression-free survival (PFS), time to response, and duration of response (DOR)

Multiple Myeloma Part 1b (QW)	

Demonstrate inactivation of MCL1 by the increase of active BAX and caspase 3 in circulating monocytes and /or the decrease of circulating monocytes in AMG 176 QW treated subjects

	

BAX and caspase 3 expression in circulating monocytes and /or circulating monocyte counts

Evaluate preliminary efficacy of AMG 176 QW when given as monotherapy in relapsed or refractory MM

	

Overall response according to IMWG-URC for MM subjects, PFS, time to response, and DOR

Acute Myeloid Leukemia Part 3a (BIW), Part 3b (QW), and Part 3c (QW)	

Evaluate preliminary efficacy of AMG 176 when given as monotherapy in relapsed or refractory AML (For Part 3c: Japan subjects only)

	

Overall response according to the 2017 European LeukemiaNet (ELN) criteria (Döhner et al, 2017) in AML subjects, event-free survival (EFS), time to response, and DOR

Acute Myeloid Leukemia Part 3d - DDI Assessment with Itraconazole in US	

Evaluate the safety and tolerability of AMG 176 when given alone and in combination with itraconazole in subjects with AML

	

Treatment-emergent adverse events and changes in vital signs, ECGs, and clinical laboratory tests

Acute Myeloid Leukemia Parts 4 and 5 (QW and BIW)	

Evaluate preliminary efficacy of AMG 176 when given in combination with azacitidine in relapsed or refractory AML

	

Overall response according to the 2017 ELN criteria in AML subjects, EFS, time to response, and DOR

